17.3.2 Secondary outcome: OAC treatment management

Table 36. Previous VKA treatment and duration according to duration since the first NOAC initiation

		≤4 months	>4 months	Total
Previous VKA	Valid N No Yes N missing			
Type of VKA	Valid N Acenocoumarol Warfarin N missing			
Years with Acenocoumarol	Valid N Mean (SD) Median (Q1-Q3) Min-Max N missing			
Years with Warfarin	Valid N Mean (SD) Median (Q1-Q3) Min-Max N missing			
Total VKA treatment duration in years	Valid N Mean (SD) Median (Q1-Q3) Min-Max N missing			

Table 37. Durations since NVAF diagnosis until first NOAC initiation, first NOAC received, first NOAC dose, dose changes and first NOAC treatment duration according to duration since the first NOAC initiation

		≤4 months	>4 months	Total
Months since NVAF diagnosis until first NOAC initiation	Valid N Mean (SD) Median (Q1-Q3)			

Document: H:\HOR-Europe\2019\2512352 - Study on anticoagulation management - BI\Proyecto\Estadística\SAP\SAP_REBELD_version1.0_08072020.docx

Author: [REDACTED] Version Number: Version 1.0
Version Date: [08072020]

Template No.: RWI_TP_BIOS0013 Revision 1

Reference: RWI_WI_BIOS0015

Effective Date: 15Jun2018

		≤4 months	>4 months	Total
	Min-Max N missing			
First NOAC received	Valid N Dabigatran Rivaroxaban Apixaban Edoxaban N missing			
First NOAC dose: Dabigatran	Valid N 110mg BID 150mg BID N missing			
First NOAC dose: Rivaroxaban	Valid N 15mg QD 20mg QD N missing			
First NOAC dose: Apixaban	Valid N 2.5mg BID 5mg BID N missing			
First NOAC dose: Edoxaban	Valid N 30mg QD 60mg QD N missing			
Changes in first NOAC dose	Valid N No Yes (increase) Yes (decrease) N missing			
First NOAC treatment duration in years*	Valid N Mean (SD) Median (Q1-Q3) Min-Max N missing			
Reason for first NOAC treatment discontinuation*	Valid N Lack of effectiveness Investigator decision			

Document: H:\HOR-Europe\2019\2512352 - Study on anticoagulation management - BI\Proyecto\Estadistica\SAP\S
AP_REBELD_version1.0_08072020.docx

Author: Version Number: Version 1.0
Version Date: [08072020]

Template No.: RWI_TP_BIOS0013 Revision 1

Reference: RWI_WI_BIOS0015

Effective Date: 15Jun2018

		≤4 months	>4 months	Total
	Patient decision Adverse event N missing			
Reason for first NOAC treatment change dose*	Valid N Lack of effectiveness Investigator decision Patient decision Adverse event N missing			

BDI: twice a day; QD: once a day

*Only patients who stopped first NOAC treatment

Table 38. Number of switches to a new NOAC and reason for switches according to duration since the first NOAC initiation

		≤4 months	>4 months	Total
Number of switches to a new NOAC	Valid N Mean (SD) Median (Q1-Q3) Min-Max N missing			
Number of switches to a new NOAC	Valid N 0 1 2 3 ... N missing			
Switchers	Valid N* Dabigatran to Rivaroxaban Dabigatran to Apixaban Dabigatran to Edoxaban Rivaroxaban to Dabigatran Rivaroxaban to Apixaban Rivaroxaban to Edoxaban			

Document: H:\HOR-Europe\2019\2512352 - Study on anticoagulation management - BI\Proyecto\Estadistica\SAP\S
AP_REBELD_version1.0_08072020.docx

Author: [REDACTED] Version Number: Version 1.0
Version Date: [08072020]

Template No.: RWI_TP_BIOS0013 Revision 1

Reference: RWI_WI_BIOS0015

Effective Date: 15Jun2018

		≤4 months	>4 months	Total
	Apixaban to Dabigatran Apixaban to Rivaroxaban Apixaban to Edoxaban Edoxaban to Dabigatran Edoxaban to Rivaroxaban Edoxaban to Apixaban N missing			
Reason for switch	Valid N* Lack of effectiveness Investigator's decision Patient's decision Adverse effect N missing			

*Valid N corresponds to the total of switches

Table 39. New NOAC received, new NOAC dose and new NOAC treatment duration according to duration since the first NOAC initiation (SECOND NOAC)

		≤4 months	>4 months	Total
Second NOAC received	Valid N Dabigatran Rivaroxaban Apixaban Edoxaban N missing			
Second NOAC dose: Dabigatran	Valid N 110mg BID 150mg BID N missing			
Second NOAC dose: Rivaroxaban	Valid N 15mg QD 20mg QD N missing			
Second NOAC dose: Apixaban	Valid N 2.5mg BID 5mg BID N missing			

Document: H:\HOR-Europe\2019\2512352 - Study on anticoagulation management - BI\Projecto\Estadistica\SAP\S
AP_REBELD_version1.0_08072020.docx

Author: [REDACTED] Version Number: Version 1.0
Version Date: [08072020]

Template No.: RWI_TP_BIOS0013 Revision 1

Reference: RWI_WI_BIOS0015

Effective Date: 15Jun2018

		≤4 months	>4 months	Total
Second NOAC dose: Edoxaban	Valid N 30mg QD 60mg QD N missing			
Changes in second NOAC dose	Valid N No Yes (increase) Yes (decrease) N missing			
Second NOAC treatment duration in years*	Valid N Mean (SD) Median (Q1-Q3) Min-Max N missing			
Reason for second NOAC treatment discontinuation*	Valid N Lack of effectiveness Investigator decision Patient decision Adverse event N missing			
Reason for second NOAC treatment change dose*	Valid N Lack of effectiveness Investigator decision Patient decision Adverse event N missing			

BDI: twice a day; QD: once a day

*Only patients who stopped second NOAC treatment

Table 39. will be repeated for each treatment switch during follow-up.

Document: H:\HOR-Europe\2019\2512352 - Study on anticoagulation management - BI\Proyecto\Estadística\SAP\S
AP_REBELD_version1.0_08072020.docx

Author: [REDACTED]

Version Number:

Version 1.0

Version Date:

[08072020]

Template No.: RWI_TP_BIOS0013 Revision 1

Reference: RWI_WI_BIOS0015

Effective Date: 15Jun2018

Table 40. Total time (in years) in NOAC treatment

		≤4 months	>4 months	Total
Total time in NOAC treatment (in years)	Valid N Mean (SD) Median (Q1-Q3) Min-Max N missing			
Total time in NOAC treatment (cat)	Valid N <1 year 1-2 years 2-3 years >3 years N missing			

Table 41. History and current antiplatelet treatment according to duration since the first NOAC initiation

		≤4 months	>4 months	Total
Antiplatelet treatments received (all)	Valid N Aspirin Clopidogrel Prasugrel Ticlopidine Ticagrelor Cilostazol Triflusal Dipyridamole Others N missing			
Time in treatment with antiplatelet agents (in years)	Valid N Mean (SD) Median (Q1-Q3) Min-Max N missing			
Current antiplatelet treatment (at study visit)	Valid N None			

Document: H:\HOR-Europe\2019\2512352 - Study on anticoagulation management - BI\Proyecto\Estadistica\SAP\S AP_REBELD_version1.0_08072020.docx

Author: [REDACTED] Version Number: Version 1.0
Version Date: [08072020]

Template No.: RWI_TP_BIOS0013 Revision 1

Reference: RWI_WI_BIOS0015

Effective Date: 15Jun2018

		≤4 months	>4 months	Total
	Aspirin			
	Clopidogrel			
	Prasugrel			
	Ticlopidine			
	Ticagrelor			
	Cilostazol			
	Triflusal			
	Dipyridamole			
	Others			
	N missing			

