14.3.2 OAC treatment management

For OAC treatment management, descriptive analysis of previous VKA treatment (yes/no), VKA treatment duration in years, first NOAC treatment duration, first NOAC dose and dose changes, new NOAC treatment duration, new NOAC dose and dose changes. Duration since NVAF diagnosis until first NOAC initiation and total time in NOAC treatment will be described. Also, the reason for switches, the number of patients that switched their first or further NOAC and mean number of switches will be presented. Antiplatelet use will be also summarized.

Document:	H:\HOR-Europe\2019\2512352 - Study on anticoagulation management - BI\Proyecto\Estadistica\SAP\SAP_REBELD_version1.0_08072020.docx		
Author:	██████████	Version Number:	Version 1.0
		Version Date:	[08072020]

Template No.: RWI_TP_BIOS0013 Revision 1

Reference: RWI_WI_BIOS0015

Effective Date: 15Jun2018

The subgroup analysis of these outcomes by the duration since the first NOAC initiation until the study visit date (> 4 months / ≤ 4 months) will also be performed. For this subgroup analysis, a minimum of 50 patients is required for each group.

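### In SAP Tables 37 and 39 the dose-change-reason row is limited to patients who stopped the NOAC, so it does not describe the dose changes counted in the same table

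*SAP*

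**What the plan says.** SAP 14.3.2 lists what is to be described for secondary outcome 2, including "first NOAC dose and dose changes, new NOAC treatment duration, new NOAC dose and dose changes". It sets no restriction to patients who stopped a drug.

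The mock tables in SAP 17.3.2 carry this out. In Table 37 the row "Changes in first NOAC dose" (no, increase, decrease) has no asterisk. The row "Reason for first NOAC treatment change dose" has one, and the footnote reads "Only patients who stopped first NOAC treatment". Table 39 has the same layout for the second NOAC: "Changes in second NOAC dose" is unstarred, "Reason for second NOAC treatment change dose" is starred, and the footnote is "Only patients who stopped second NOAC treatment". A note says that Table 39 "will be repeated for each treatment switch during follow-up", so the restriction passes to third and later NOACs.

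In both tables the asterisk also sits on the treatment-duration row and on the discontinuation-reason row.

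**The concern.** A dose change happens while the patient stays on the same drug; SAP 7.2.12 defines a switch separately, as a move to another NOAC. Stopping is therefore the right condition for a discontinuation reason and the wrong one for a dose-change reason, whose natural denominator is the patients, or the changes, with a dose change on that NOAC.

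As specified, one table would show how many doses were raised or lowered on a NOAC and then give reasons from a different, selected group: dose changers who later gave up that NOAC. A reader would naturally take the reasons as explaining the counts, and they would not. The gap falls on the patients the study is about, those still on their NOAC at the visit.

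**Working it through.** The plan states no figure that bears on this point, so the check is to trace the footnote and work out who can enter each row.

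1. **Who is in the dose-change row.** It is unstarred in both tables, so it covers all patients who took that NOAC. Let D be the number with a dose change on it.
2. **Who is in the reason row.** It is starred, so it covers only those of the D who stopped that NOAC. Call this number S; S cannot exceed D.
3. **What is left out.** D − S patients have their dose change counted but no reason tabulated. As a share this is 1 − S/D.
4. **The NOAC being taken at the visit.** Every patient in the full analysis set is on a NOAC at the visit (Protocol 9.2.2 and SAP 6.2, inclusion criterion 4). SAP 7.2.9 uses the visit date as the stop date of an unfinished first NOAC and labels such patients censored; SAP 7.2.10 and 7.2.11 use the visit date in the same way. That date serves the duration calculation and does not record a stop. For the current NOAC, S is therefore 0, apart from the case in step 5. For a patient who never switched, the first NOAC is the current one, so this applies to Table 37 as well as to Table 39 and its repeats.
5. **A possible exception.** SAP 7.2.11 foresees interruptions of NOAC treatment. A patient who interrupted and resumed the same drug might be counted as having stopped it. The footnotes do not say.
6. **Whether the reasons appear elsewhere.** Table 38 gives reasons for switches. Tables 27 to 35 and 50 give the current dose, and Table 51 the dosing category, without reasons for a change. Tables 54 to 57 list a reduced or increased dose as action taken, but only for adverse drug reactions to Pradaxa. No visible table gives dose-change reasons without the restriction.
7. **Whether S/D can be estimated.** It needs the share of dose changers who later stopped that NOAC. Neither document gives a dose-change rate, a stopping rate or the link between them. The share left out is 0 if every dose changer later stopped and 1 if none did; the documents do not narrow that range.
8. **Whether the restriction looks deliberate.** The same asterisk on the duration rows conflicts with SAP 7.2.9 and 7.2.10, which include unfinished NOACs up to the visit. This suggests that a footnote meant for the discontinuation row was applied too widely.

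**The case against.** The strongest reply is that nothing required is lost. Secondary objective 2 (Protocol 8, SAP 3.2) and the outcome and analysis text (Protocol 9.3.2.2 and 9.7.1, SAP 14.2.2 and 14.3.2) ask for dose changes and for reasons for switching. Dose changes are fully counted in the unstarred rows, and Table 38 gives switch reasons without this restriction. The affected row is an addition made in the mock tables. This stands, and it limits the severity. A reader might infer that a secondary objective goes unreported; the documents do not support that.

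Three other inferences also go too far:

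- **That most reasons are lost.** Any percentage, such as a loss of 70% to 95%, is only one minus an assumed stopping rate of 30% to 5%, and it assumes that stopping is unrelated to having had a dose change.
- **That the reasons shown would lean towards adverse events or lack of effectiveness.** This is plausible for patients who later stopped, but neither document shows it.
- **That the reasons are certainly in the database.** The protocol's variable lists name dose changes and reasons for switch, not reasons for dose change, and the CRF is not among the documents. SAP 4.6 records that another planned reason, for switching from a VKA, was not specifically collected.

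None of this makes the row right as written. If the plan means to show reasons for dose change, their denominator should be the dose changes.

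**Conclusion.** The point holds as a wrong denominator in a planned descriptive output of secondary outcome 2. As footnoted, Tables 37 and 39 give reasons only for dose changers who stopped that NOAC. They omit reasons for dose changes on a NOAC still being taken, with the possible exception of an interruption and restart, so the reason row does not match the dose-change row in the same table.

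Severity is modest. The primary outcome, the dose-change counts and the switch reasons are unaffected. The size of the omission cannot be computed from the documents. The conclusion rests on reading stopped in its ordinary sense and on the visible tables; Table 44 is not visible.

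**What to change.** In Table 37, and in Table 39 with its repeats:

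- Remove the asterisk from the dose-change-reason row and give it its own footnote: all patients with a dose change on this NOAC, whether or not it was later stopped.
- State whether the row counts patients or dose changes, as Table 38 does for switches. If it counts dose changes, Valid N plus N missing should equal the total number of dose changes. The sum of the increase and decrease counts is not a safe check when the unit is patients, because one patient may have had both.
- Count reasons that the CRF did not collect as N missing.
- Keep the restriction to stoppers on the discontinuation-reason row.
- In the same edit, resolve the asterisk on the duration rows against SAP 7.2.9 and 7.2.10.

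The cost is a footnote change in two mock tables and the matching programming. How complete the reason row then is depends on what the CRF collected, which should be checked first.

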17.3.3 Secondary outcome: Clinical Frailty Scale

Table 42. Clinical Frailty Scale grading at the time of the study visit according to current NOAC type

		Dabigatran	Rivaroxaban	Apixaban	Edoxaban	Total
CFS score	Valid N					
	1-Very fit					
	2-Well					
	3-Managing well					
	4-Vulnerable					
	5-Mildly frail					
	6-Moderately frail					
	7-Severely frail					
	8-Very severely frail					
	9-Terminally ill					
	N missing					
CFS (categorized)	Valid N					
	Non-frailty patients (CFS scoring ≤4)					
	Frailty patients (CFS scoring >4)					
	N missing					

Document: H:\HOR-Europe\2019\2512352 - Study on anticoagulation management - BI\Proyecto\Estadistica\SAP\S AP_REBELD_version1.0_08072020.docx

Author: [REDACTED] Version Number: Version 1.0
Version Date: [08072020]

Template No.: RWI_TP_BIOS0013 Revision 1

Reference: RWI_WI_BIOS0015

[figure not shown]
Effective Date: 15Jun2018

17.3.4 Secondary outcome: Prevention strategy

Table 43. First NOAC usage at the time of first NOAC initiation according to current NOAC type

		Dabigatran	Rivaroxaban	Apixaban	Edoxaban	Total
Reason for prescription of the first NOAC	Valid N Primary prevention Secondary prevention N missing					

Document: H:\HOR-Europe\2019\2512352 - Study on anticoagulation management - BI\Proyecto\Estadistica\SAP\SAP_REBELD_version1.0_08072020.docx

Author: [Redacted]

Version Number:

Version 1.0

Version Date:

[08072020]

Template No.: RWI_TP_BIOS0013 Revision 1

Reference: RWI_WI_BIOS0015

Effective Date: 15Jun2018

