8. RESEARCH QUESTION AND OBJECTIVES

This study has been designed in order to describe the current non-vitamin K antagonist oral anticoagulants (NOACs) management in elderly patients in Spain.

Primary objective: To describe the pattern of usage of NOACs prescribed according to their Summary of Product Characteristics (SmPC), by current NOAC type and dose, in elderly patients (≥ 75 years-old) with non-valvular atrial fibrillation (NVAF) at the time of the study visit.

Secondary objectives:

1. To describe patients characteristics at the time of the study visit by current NOAC type stratified by duration since first NOAC initiation.
2. To describe OAC treatment management since first NOAC initiation until the study visit by duration since first NOAC initiation: previous vitamin K antagonists (VKA) treatment, first NOAC treatment duration, dose changes, switch between NOACs and reasons for switch, total NOAC treatment duration and additional antiplatelet treatment.
3. To describe the Clinical Frailty Scale grading, CFS ([19](#)), at the time of the study visit, by current NOAC type.
4. To describe first NOAC usage by NOAC type, for primary prevention or secondary prevention, at the time of first NOAC initiation.

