4.6 Changes to Analysis from Protocol

Per protocol, the variable “reason for VKA switch will be described under the OAC treatment management outcome. Finally, reason for VKA treatment switch has not been collected specifically in the VKA section of the CRF. This has been deleted from section 14.2.2 of SAP.

New analysis not included in the final protocol have been considered:

- Antiplatelet treatment according to current NOAC type
- Treatment received at the moment of thromboembolic and bleeding events.
- For all NOACs, the different doses that patients take according to HAS-BLED score.
- Underdosed and overdosed patients (for current NOAC treatment).
- HAS-BLED total score according to NOAC and antiplatelet current treatment.
- Multivariate model to evaluate the association between the Clinical Frailty Scale (dependent variable) and the thromboembolic and the bleeding events (independent variables). To calculate this analysis, only events that have occurred subsequent to the start of anticoagulant therapy (not those prior to the start of VKA / NOACs) will be considered. Univariate analysis will be performed. All variables which have a P value of less than 0.1 will be included in the multivariate analysis.

Document:	H:\HOR-Europe\2019\2512352 - Study on anticoagulation management - BI\Proyecto\Estadistica\SAP\S		
	AP_REBELD_version1.0_08072020.docx		
Author:	██████████	Version Number:	Version 1.0
		Version Date:	[08072020]

Template No.: RWI_TP_BIOS0013 Revision 1

Reference: RWI_WI_BIOS0015

Effective Date: 15Jun2018

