7.2.9 Duration of first NOAC treatment

The duration of the first NOAC treatment will be calculated as the number of years (or months, depending on the data) between stop date and start date for the NOAC treatment with the minimum start date:

Duration of the first NOAC (years) = (stop date of first NOAC – start date of first NOAC + 1)/(365.25)

or

Duration of the first NOAC (months) = (stop date of first NOAC – start date of first NOAC + 1)/(30.5)

In the case the first NOAC has not been finished, the study visit date will be considered as the stop date (censored cases).

Document:	H:\HOR-Europe\2019\2512352 - Study on anticoagulation management - BI\Proyecto\Estadistica\SAP\S		
	AP_REBELD_version1.0_08072020.docx		
Author:	██████████	Version Number:	Version 1.0
		Version Date:	[08072020]

Template No.: RWI_TP_BIOS0013 Revision 1

Reference: RWI_WI_BIOS0015

Effective Date: 15Jun2018

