7.2.10 Duration of new NOAC treatments

The duration of new NOAC treatment will be calculated as the number of years (or months, depending on the data) between stop date and start date for the new NOAC treatment:

$$\text{Duration of the new NOAC (years)} = (\text{stop date of new NOAC} - \text{start date of new NOAC} + 1) / (365.25).$$

or

$$\text{Duration of the new NOAC (months)} = (\text{stop date of new NOAC} - \text{start date of new NOAC} + 1) / (30.5).$$

In the case the new NOAC has not been finished, the study visit date will be considered as the stop date.

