7.2.11 Total time in NOAC treatment

NOAC treatment duration in years will be calculated as the sum of the years of each NOAC treatment. The duration of the each NOAC treatment will be calculated as:

$$\text{Duration of each NOAC (years)} = (\text{stop date of NOAC} - \text{start date of NOAC} + 1) / (365.25).$$

For the last NOAC treatment (receiving at study visit) the stop date will be the study visit date.

In other hand, in the case there are periods of interruption of the NOAC treatment, only the time that they have been in treatment will be considered. In this case, the time in each period will be calculated from the previous formula, adding the different periods in treatment.

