14.2.4 Prevention strategy

The first NOAC usage by NOAC type, for primary prevention or secondary prevention, at the time of first NOAC initiation.

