14.3.4 Prevention strategy

[figure not shown]
First NOAC usage will be described by NOAC type, for primary prevention or secondary prevention, at the time of first NOAC initiation.

Document: H:\HOR-Europe\2019\2512352 - Study on anticoagulation management - BI\Proyecto\Estadística\SAP\SAP_REBELD_version1.0_08072020.docx
Author: [REDACTED] Version Number: Version 1.0
Version Date: [08072020]

Template No.: RWI_TP_BIOS0013 Revision 1

Reference: RWI_WI_BIOS0015

Effective Date: 15Jun2018

Document: H:\HOR-Europe\2019\2512352 - Study on anticoagulation management - BI\Proyecto\Estadistica\SAP\S
AP_REBELD_version1.0_08072020.docx

Author: [Redacted]

Version Number: Version 1.0

Version Date: [08072020]

Template No.: RWI_TP_BIOS0013 Revision 1

Reference: RWI_WI_BIOS0015

Effective Date: 15Jun2018

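### Mock Tables 37 and 39 limit NOAC duration to patients who stopped, against SAP 7.2.9 and 7.2.10, and Table 43 groups the reason for the first NOAC by current rather than first drug

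*SAP*

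**What the plan says.** **Duration.** For an ongoing first NOAC, SAP 7.2.9 states: "In the case the first NOAC has not been finished, the study visit date will be considered as the stop date (censored cases". SAP 7.2.10 has the same rule for later drugs: "In the case the new NOAC has not been finished, the study visit date will be considered as the stop date". SAP 14.3 sets the FAS for all secondary outcomes, and 14.3.2 names first and new NOAC duration among the quantities to describe. In mock Tables 37 and 39 (SAP 17.3.2) the duration row carries an asterisk. The footnote restricts asterisked rows to patients who stopped the first or second NOAC respectively. The same asterisk is on the rows for discontinuation reason and dose-change reason, but not on the row that counts dose changes. Table 39 is to be repeated for each switch.

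**Prevention strategy.** Protocol section 8, objective 4, reads: "To describe first NOAC usage by NOAC type, for primary prevention or secondary prevention, at the time of first NOAC initiation". SAP 14.3.4 repeats it as the analysis: "First NOAC usage will be described by NOAC type, for primary prevention or secondary prevention, at the time of first NOAC initiation". Mock Table 43 (SAP 17.3.4) tabulates the reason for prescribing the first NOAC, primary or secondary prevention, under the title "First NOAC usage at the time of first NOAC initiation according to current NOAC type".

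**The concern.** Programmers build from mock tables. Where a mock table and the SAP text disagree, someone must choose, and the choice may go unrecorded.

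For duration, restricting to stoppers selects short spells. Every eligible patient is on a NOAC at the visit (Protocol 9.2.2, inclusion criterion 4), so the footnote removes those still on the drug, who may be most of the sample. The mean of the remaining spells would sit in a row named simply as first or second NOAC treatment duration.

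For Table 43, the reason was recorded for one drug and the columns may name another. A by-drug comparison of primary and secondary prevention would then mix first-drug reasons across columns, and any real difference between drugs would tend to be blurred.

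**Working it through.** The plan states no figure here to reproduce. The check is mainly a comparison of texts; the arithmetic only illustrates size.

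**1. Duration rows**

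| Source | Patients in the duration row | Ongoing spell |
|---|---|---|
| SAP 7.2.9, 7.2.10 | all who received that NOAC | kept, visit date as stop date |
| Tables 37, 39 footnotes | those who stopped that NOAC | dropped |

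Under the footnote, the visit-date rule has nobody to apply to in these rows. In the last repeat of Table 39 nobody has a further switch, so everyone in it is still on that drug at the visit. Its duration row is therefore empty if stopping means permanent stopping. The SAP does not define stopping. SAP 7.2.11 foresees breaks in treatment ("in the case there are periods of interruption of the NOAC treatment, only the time that they have been in treatment will be considered"), so a patient who paused and restarted the same drug might be counted.

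**2. Table 43**

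Objective 4, SAP 14.2.4 and SAP 14.3.4 fix the time point at first initiation and do not mention the current drug. Objectives 1 and 3, SAP 14.2.3 and SAP 14.3.1 do name the current drug. In the same list of objectives, the natural reading of number 4 is therefore the first NOAC. The two drugs can differ: SAP 14.2.2 counts switches and Table 38 lists all twelve drug-to-drug pairs. Patients who never switched, or who returned to their first drug, are in the right column, and the Total is unaffected. Table 37 shows the first NOAC received, but by duration stratum and without prevention type. Among the tables that can be seen, none crosses first NOAC with prevention type.

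**3. Illustration (all rates assumed; only the planned 500 is from the documents)**

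Let s be the share who switched away from the first NOAC, none of whom returned, with no interruptions.

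- Table 37 duration N under the footnote = 500 × s, against 500 under 7.2.9. The same 500 × s patients sit off-column in Table 43.
- Mean duration: visits uniform from 0.25 to 6 (or 0.25 to 3) years after first NOAC start, time C; exponential time to stopping, T, with the hazard set so that P(T < C) = s. The footnote mean is E[T | T < C]; the 7.2.9 mean is E[min(T, C)].
- Table 43: equal drug shares; switches spread evenly over the other three drugs; secondary prevention 30% for drug A and 20% for the rest. Column A = (1 − s) × 0.30 + s × 0.20. Any other column = (1 − s) × 0.20 + (s/3) × (0.30 + 0.20 + 0.20). Gap = 10 × (1 − 4s/3) points, against a true 10.

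| Assumed s | 5% | 15% | 30% |
|---|---|---|---|
| N in Table 37 duration row (7.2.9: 500) | 25 | 75 | 150 |
| Mean years, visits to 6 y: footnote / 7.2.9 | 1.97 / 3.02 | 1.90 / 2.82 | 1.78 / 2.49 |
| Mean years, visits to 3 y: footnote / 7.2.9 | 0.99 / 1.57 | 0.96 / 1.47 | 0.90 / 1.31 |
| Gap shown in Table 43 (true 10 points) | 9.3 | 8.0 | 6.0 |

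The footnote mean is 63% to 71% of the 7.2.9 mean (0.99/1.57 to 1.78/2.49), that is, 29% to 37% shorter.

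**The case against.** **Objective 4 is not answered at all.** A reader might infer this from Table 43, but the documents do not establish it. The visible mock tables go from Table 43 to Table 45, and what Table 44 contains cannot be known. The statement must stay limited to the tables that can be seen.

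**Table 43 flatly contradicts the text, or mislabels its data.** Neither holds. The text refers to NOAC type without adding the word first, so the mismatch rests on the natural reading, strong as that is. The title states its columns openly. The problem is the grouping variable, not the population: the same patients are in the table. Section 4.6, which lists additions under "New analysis not included in the final protocol have been considered", does not mention this grouping. That adds little, because a drafting slip would not be listed there.

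**Completed spells are a legitimate summary, and the footnote discloses it.** This is fair as far as it goes: 7.2.9 itself calls ongoing spells censored, and the footnote and valid N would be printed. But disclosure does not settle which instruction governs, and 7.2.9 says ongoing spells are counted.

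**Little information is lost.** This stands in part. For a patient with no switch and no interruption, the 7.2.9 duration equals total NOAC time, which Table 40 reports for everyone. The figures above rest on assumed rates and are not evidence about this study.

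**Conclusion.** Both points hold, at minor severity. The conflict in Tables 37 and 39 is explicit: the SAP text keeps ongoing treatment and the footnotes remove it. The Table 43 mismatch holds on the natural reading of objective 4 and of SAP 14.2.4 and 14.3.4.

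The effect is confined to descriptive secondary outcomes, namely first and new NOAC duration under objective 2 and prevention strategy by drug under objective 4. The primary outcome and study size are untouched.

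The direction for duration is clear when switching is the main way of stopping: a stoppers-only mean runs short as a description of the FAS. Its size, and the blurring in Table 43, depend on switch, return and interruption rates that the documents do not give. An empty last repeat of Table 39 follows only if stopping means permanent stopping.

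**What to change.** - **Tables 37 and 39, duration rows:** remove the asterisk so that the rows follow 7.2.9 and 7.2.10. Completed and ongoing spells may also be shown separately.
- **Definition:** state in one sentence whether an interruption followed by restart of the same drug counts as a stop.
- **Reason rows:** keep the footnote on the discontinuation-reason rows. On the dose-change-reason rows it would drop dose changes in patients still on the drug, so use patients with a dose change as the denominator there.
- **Table 43:** head the columns by first NOAC received, a variable already in Table 37. A version by current NOAC is optional and should be labelled as such.

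The cost is one column heading, a few asterisks, one denominator note and one sentence. No new data or method is needed, and it is best done before programming.
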